#### 9.4 Follow-up visits

The following procedures are performed at all scheduled follow-up visits:

- Complete physical examination, including weight, vital signs, and clinical assessments of head, ears, eyes, nose, and throat; neck; lymph nodes; heart; chest; abdomen; extremities; neurological function; and skin;
- Specimen collection;
- Risk reduction counseling (as described in Section 9.5);
- Pregnancy prevention assessment (as described in Section 9.2 and 9.6);
- Assessment of new or unresolved social impacts (site staff will ask participant about the status of any unresolved social impacts and if s/he has experienced any new social impacts as a result of the trial participation);
- Assessment of new or continuing concomitant medications (as described in Section 9.2); and
- Assessment of new or unresolved AEs/intercurrent illnesses.

Additional procedures will be performed at scheduled follow-up visits as specified in [Appendix F](#):

- Administration of the social impact assessment questionnaire (types of impacts assessed involve personal relationships, health insurance, life insurance, educational or employment opportunities, housing, immigration, or travel);
- HIV infection assessment including pretest counseling and HIV testing. A subsequent follow-up contact is conducted to provide post-test counseling and to report results to participant;
- Confirm that participants received HIV test results from previous visit. If not, provide test results and post-test counseling as appropriate;
- SLE assessment, as determined by a rheumatologist or designee, using standard instruments for this purpose (SELENA-SLEDAI, including Complement profile [C3/C4/CH50] and anti-dsDNA); and functional status assessment by a staff member using RAPID3;

- CBC/differential/platelets;
- Urinalysis (see Section 9.7);
- Urine or serum pregnancy test (for participants who were assigned female sex at birth), in accordance with local regulatory requirements. Persons who are NOT of reproductive potential due to having undergone total hysterectomy or bilateral oophorectomy (verified by medical records), are not required to undergo pregnancy testing; and
- Health contact (see HVTN 121 SSP).

## 9.5 HIV counseling and testing

HIV counseling will be performed in compliance with the CDC's guidelines or other local guidelines for HIV counseling and referral. HIV testing will be performed in accordance with the current HVTN HIV testing algorithm following enrollment.

Participants will be counseled routinely during the trial on the avoidance of HIV infection and on the potential negative social impacts of testing antibody positive due to the vaccine. They will also be counseled on the risks of HIV antibody testing outside of the HVTN CRSs and will be discouraged from doing so during study participation and/or during any period of vaccine-induced positive serology.

Study staff will take particular care to inform study participants of the likelihood of routine HIV testing being offered or performed outside the study CRS at emergency rooms, clinics, and medical offices. Such testing has become more likely due to the CDC's revised guidelines for HIV counseling and testing, as well as policy changes in many countries to make HIV testing more frequent and routine. CRS staff should inform participants of their right to opt out of HIV testing outside the study site. CRS staff should inform study participants if local and/or state policies and regulations permit medical providers to perform HIV testing without first informing patients. If this is the case, then CRS staff should advise study participants that they may decline testing preemptively. CRS staff should also inform participants if positive results must be reported to local public health authorities. CRS staff should provide participants with CRS contact information and should encourage participants to ask medical providers to contact the CRS. The CRS can verify that the participant is in an HIV vaccine clinical trial and should only be tested at the study CRS.

Potential participants identified as being HIV-infected during screening are not enrolled. Potential and enrolled participants identified as being HIV-infected will be referred for medical treatment, counseling, and management of the HIV infection. Participants who are found to be HIV-infected after enrollment will not receive any additional study product but will continue to be followed in the study

for safety assessments. These individuals may also be referred to appropriate ongoing clinical trials or observational studies.

### 9.5.1 Distinguishing intercurrent HIV infection from vaccine-induced positive serology

The AIDSVAX B/E® study product may elicit an antibody response to HIV proteins. Therefore, vaccine-induced positive serology may occur in this study. Several precautionary measures will be taken to distinguish intercurrent HIV infection from vaccine-induced positive serology. These precautionary measures include:

- Participants will have physical examinations at visits specified in [Appendix F](#). Signs or symptoms of an acute HIV infection syndrome, an intercurrent illness consistent with HIV-1 infection, or probable HIV exposure would prompt a diagnostic workup per the HVTN algorithm for Recent Exposure/Acute Infection Testing to determine HIV infection.
- HIV testing will be performed at multiple timepoints throughout the study (see [Appendix E](#)). The Laboratory Program (or approved diagnostic laboratory) will follow the HVTN HIV testing algorithm (see *Study Specific Procedures*), which is able to distinguish vaccine-induced antibody responses from actual HIV infections.
- All participants can receive HIV-1 diagnostic testing from the site following their last scheduled visit until they are told they do not have vaccine-induced seropositivity.
- All participants who received vaccine product and who have vaccine-induced positive or indeterminate HIV-1 serology (as measured by the standard anti-HIV antibody screening tests) at the end of study will be offered poststudy HIV-1 diagnostic testing (per the HVTN poststudy HIV-1 testing algorithm) periodically and free of charge as medically/socially indicated (approximately every 6 months) unless or until HIV antibody testing is no longer the standard test in clinical settings.

### 9.5.2 Vaccine-induced seropositivity (VISP) registry

Experimental HIV vaccines may induce antibody production to HIV antigens, producing reactive results on commercially available HIV test kits. This is called “vaccine-induced seropositivity” (VISP). In order to provide poststudy HIV testing to distinguish between VISP and HIV infection, and to mitigate potential social harms resulting from VISP in HIV vaccine recipients who are not infected with HIV, the HVTN has created a VISP registry. At the end of the study, the registry will allow trained staff to verify that an individual has received an HIV vaccine, and therefore has the potential for VISP. Information in the VISP registry will not be used for research. Rather, the registry exists to support provision of poststudy testing and counseling services to HIV vaccine recipients. The registry

contains the names of all study participants, unless they request that their names be removed.

## 9.6 Contraception status

Contraception status is assessed and documented at every scheduled clinic visit for a participant who was assigned female sex at birth and who is sexually active in a way that could cause that participant to become pregnant. Prior to enrollment and throughout the study, staff will ask participants to verbally confirm their use of adequate contraceptive methods. A participant who was assigned female sex at birth and is sexually active in a way that could cause that participant to become pregnant should be reminded at all scheduled clinic visits of the importance of using contraception and should be referred to specific counseling, information, and advice as needed (specific contraception requirements are listed in Section 7.1). This reminder should be documented in the participant's study record.

Self-reported infertility—including having reached menopause (no menses for 1 year) or having undergone hysterectomy, bilateral oophorectomy, or tubal ligation—must be documented in the participant's study record.

## 9.7 Urinalysis and urine protein:creatinine ratio

A complete urinalysis with microscopy is performed on urine obtained by clean catch. Spot urine protein:creatinine ratio will also be performed.

If the screening urinalysis is transiently abnormal due to menses or infection, document this issue in the participant's source documentation. For infection, provide appropriate treatment and/or referral. Following resolution, repeat the urinalysis and, if within the eligibility limits specified in the protocol, the participant may be enrolled.

Follow-up urinalysis should be deferred if a participant is menstruating, but should be performed as soon as possible. If a follow-up urinalysis is abnormal due to a participant's menstrual period, document in the comment section of the case report form (CRF) and repeat the urinalysis once the participant is no longer menstruating.

## 9.8 Assessments of reactogenicity

For all participants, baseline assessments are performed before and reactogenicity assessments are performed after each vaccination. All reactogenicity symptoms are followed until resolution and graded according to the DAIDS Table for Grading the Severity of Adult and Pediatric Adverse Events, Corrected Version 2.1, July, 2017, except as noted in Section 11.2.2.

The reactogenicity assessment period is 7 full days following each vaccination per the assessment schedule shown in [Table 9-1](#). Participants are instructed to record symptoms using a Participant Diary. Contact between the participant and the site staff should take place at least once within 72 hours/3 days postvaccination. In general, a participant who self-reports any postvaccination reaction greater than mild is seen by a clinician within 48 hours after onset, unless the reaction is improving and/or has completely resolved. Clinic staff will follow new or unresolved reactogenicity symptoms present at day 7 to resolution. Participants are instructed to contact the clinic for events that arise during the period between vaccination and the next scheduled visit.

Reactogenicity events are reported using CRFs that correspond to the time of assessment in [Table 9-1](#). Reactogenicity assessments include assessments of systemic and local symptoms and vaccine-related lesions. Events not listed on a CRF, or with an onset after the reactogenicity assessment period (day of vaccination and 7 full days after), or those meeting SAE/AEs requiring expedited reporting to DAIDS criteria, are recorded on an adverse experience log form.

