#### **4.1.2 Safety considerations for immunization of persons with SLE**

Data on the safety of vaccines in persons with SLE are readily available. The majority of published guidelines have emphasized the safety of killed or subunit vaccines in autoimmune disease patients (31, 32, 34, 35); and while live attenuated vaccines should be used cautiously, they also have been demonstrated to be safe in this population (34).

Vaccination of persons with SLE has been studied using a variety of immunogens and study designs. Between 1978 and 2016, there were at least 40 published studies examining vaccination in adults and children with SLE. The studies examined 2,595 persons with SLE who were vaccinated, 287 persons with SLE who were not vaccinated as a part of the published studies, and 1,169 vaccinated controls (36-77). The methods used to evaluate study participants were variable, with 29/40 using the SLE Disease Activity Index (SLEDAI). A summary of the findings follows.

- 11 studies that compared vaccinated and unvaccinated persons with SLE (including 5 randomized controlled trials) showed no difference in disease activity between groups (36-38, 42, 46, 51, 57, 67, 72, 73, 76, 77).
- 9 studies that compared disease activity pre- and post-vaccination in persons with SLE showed no significant difference in disease activity (48, 49, 52, 53, 57, 58, 63, 64, 69).
- 21 studies (including some of the above-noted studies) examined SLE disease flares post-vaccination (40, 47, 54, 56, 58, 59, 61, 67, 68).
  - 13 reported that the rate of flares among vaccinated SLE patients was similar to that among unvaccinated SLE patients (40, 42, 47, 51, 54, 56-59, 61, 67, 68, 72, 77).
  - 4 studies each reported one vaccinated SLE participant who experienced a single flare (3 glomerulonephritis, 1 optic neuritis, 1 unspecified) (55, 62, 74, 75).

- 1 reported 7/62 SLE participants experienced a flare (1 with a severe flare of glomerulonephritis and 6 with mild to moderate disease flares of varying symptoms post-influenza vaccination) (71).
- 1 recruited SLE patients with SLEDAI < 4, and reported 3/28 participants experienced a flare (rash/alopecia, photosensitivity/discoid rash, polyarthritis) (60).
- 1 reported 4/20 participants with flare (joint symptoms, vasculitis, altered affect, increased nephritis) (41).

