### 6.3.3.1 Reactogenicity

The number and percentage of participants experiencing each type of reactogenicity sign or symptom will be tabulated by severity and the percentages displayed graphically by arm. For a given sign or symptom, each participant's reactogenicity will be counted once under the maximum severity for all injection visits.

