### 9.8.1 Assessment of systemic and local symptoms

Systemic symptoms include increased body temperature, malaise and/or fatigue, myalgia, headache, chills, arthralgia, and nausea. Local symptoms include pain and/or tenderness at the injection site. The daily maximum severity reached for each symptom during the assessment period is reported.

Body temperature is measured by oral or infrared thermometry. All temperatures must be measured by non-axillary thermometry. This includes temperatures taken in the clinic, as well as temperatures taken by participants during the reactogenicity period.

Temperature is reported in degrees Celsius. If temperature is measured in Fahrenheit, the conversion to Celsius should be documented in the participant's chart note. A measurement is taken once daily during the assessment period and should be repeated if participant is feeling feverish.

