**Table 11-8 AE notification and safety pause/AE review rules**

Event and relationship to study products	Severity	HVTN CRS action a	HVTN Core action
SAE, related	Grade 5 or Grade 4	Phone immediately, email and submit forms immediately	Immediate pause
SAE, not related	Grade 5	Phone immediately, email and submit forms immediately	Immediate PSRT notification
SAE, related	Grade 3, 2, or 1	Email and submit forms immediately	Immediate PSRT notification and prompt PSRT AE review to consider pause
AE b , related	Grade 4 or 3	Email and submit forms immediately	Immediate PSRT notification and prompt PSRT AE review to consider pause
“Severe” c SLE flare, regardless of relationship	N/A	Phone immediately, email and submit forms immediately	Prompt PSRT AE review
“Mild or moderate” d,e SLE flare, related	N/A	Phone immediately, email and submit forms immediately	Prompt PSRT AE review
3 or more confirmed “moderate” or “severe” SLE flares, regardless of relatedness	N/A	Phone immediately, email and submit forms immediately	Immediate pause

a Email addresses are found on the Protocol home page on the HVTN Members’ site (<https://members.hvtn.org/protocols/hvtn121>). Phone numbers for each pause rule are in the HVTN 121 SSPs.

b Does not include the following Grade 3 subjective reactogenicity symptoms: injection site pain, tenderness, fatigue/malaise, myalgia, arthralgia, chills, headache, nausea (unless IV rehydration required).

c “Severe” SLE flare is defined by application of the SELENA-SLEDAI instrument ([Appendix G](#)).

d “Moderate” SLE flare is defined by application of the SELENA-SLEDAI instrument ([Appendix G](#)), as well as the determination by a rheumatologist that the participant has flare components/symptoms/lab indices necessitating treatment with a dosage of Prednisone (or equivalent) in the range of >7.5 mg/day to < 0.5 mg/kg/day.

e “Mild” SLE flare is defined by application of the SELENA-SLEDAI instrument ([Appendix G](#)), as well as the determination by a rheumatologist that the participant has flare components/symptoms/lab indices necessitating treatment with a dosage of Prednisone (or equivalent) of ≤7.5 mg/day.

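### A non-serious arthralgia, myalgia or fatigue that starts on days 0 to 7 after a dose stays a reactogenicity record however long it lasts, and no planned table shows its duration

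*Combined protocol and SAP*

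**What the plan says.** **Recording.** Section 9.8.1 sets the solicited list: "Systemic symptoms include increased body temperature, malaise and/or fatigue, myalgia, headache, chills, arthralgia, and nausea". Section 9.8 decides what goes to the AE log. Its sentence opens "Events not listed on a CRF, or with an onset after the reactogenicity assessment period (day of vaccination and 7 full days after" and ends "or those meeting SAE/AEs requiring expedited reporting to DAIDS criteria, are recorded on an adverse experience log form". For symptoms that outlast the window, the instruction is "Clinic staff will follow new or unresolved reactogenicity symptoms present at day 7 to resolution". No duration turns such a symptom into an AE-log entry.

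**Review.** Table 11-8 calls for immediate notification and prompt review by the Protocol Safety Review Team (PSRT) for a related Grade 3 or 4 AE. Footnote b, attached to that row only, narrows it: "Does not include the following Grade 3 subjective reactogenicity symptoms: injection site pain, tenderness, fatigue/malaise, myalgia, arthralgia, chills, headache, nausea".

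**Tabulation.** Under Section 6.3.3.1, each participant's reactogenicity for a given symptom "will be counted once under the maximum severity for all injection visits". Duration is not among the planned summaries. Section 6.3.3.4 plans box plots and summary statistics for SELENA-SLEDAI and a listing of participants who stop vaccination because of related flares. It plans no table of all flares.

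**The concern.** The recording rule sorts events by symptom name and day of onset. In people with SLE, neither separates a vaccine reaction from early disease activity. The protocol recognises the overlap. Section 6.1.1 names reactogenicity and flare as two categories of AE and treats them separately in its calculations. Exclusion criterion 25 rules out conditions whose symptoms could be mistaken for vaccine reactions, but exempts SLE, so the ambiguity is built into the cohort. The literature review in Section 4.1.2 counts joint complaints among post-vaccination flares, for example "1 reported 4/20 participants with flare (joint symptoms, vasculitis, altered affect, increased nephritis". Section 11.2.2 adapts AE grading to SLE for several conditions, but Section 9.8 has no rule for the overlapping solicited symptoms.

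At stake is whether the safety tables can show that musculoskeletal pain or fatigue began just after a dose and did not go away. Safety is a primary objective, and the trial describes itself as the first HIV vaccine trial in this population.

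**Working it through.** This is mainly a reading of rules. The arithmetic below gives coverage and scale only. Day 0 is the day of vaccination.

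**1. Apply the recording and tabulation rules to five illustrative events.**

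| Event | AE log? | Where it is summarised |
|---|---|---|
| Non-serious arthralgia, day 5 to day 6 | No | 6.3.3.1, maximum grade |
| Non-serious arthralgia, day 5 to day 65 | No | 6.3.3.1, maximum grade |
| Non-serious arthralgia, day 8 to day 9 | Yes (onset after day 7) | 6.3.3.2 |
| Serious arthralgia, onset day 5 | Yes (serious) | 6.3.3.2 |
| Diagnosed flare or arthritis, onset day 5 | Yes (not a listed symptom) | 6.3.3.2, plus the flare rows of Table 11-8 |

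The first two rows give the same table entry. A one-day ache starting on day 8 is a logged AE, and a 60-day ache starting on day 5 is not. This assumes that reactogenicity forms do not feed the MedDRA tables of Section 6.3.3.2. The protocol tabulates the two separately and does not say that they do.

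**2. Check what the SLE assessments cover.** Appendix F schedules them on days 0, 7, 14, 28, 35, 42, 84, 168, 175, 182 and 238. Appendix G scores the visit day and the 10 days before it.
- Dose 1 (day 0): day 7 reaches back past day 0 and day 14 covers days 4 to 14, so days 0 to 14 are covered.
- Dose 2 (day 28): day 35 covers 25 to 35 and day 42 covers 32 to 42, so days 28 to 42 are covered.
- Dose 3 (day 168): day 175 covers 165 to 175 and day 182 covers 172 to 182, so days 168 to 182 are covered.
- Later: day 84 reaches back to 74 and day 238 to 228. Days 43 to 73 and 183 to 227 fall in no scheduled assessment.

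A flare that can be scored within two weeks of a dose therefore meets a scheduled assessment. A symptom that lingers after doses 2 or 3 may run through an uncovered stretch.

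**3. Check which symptoms can score (Appendix G).**
- Arthritis needs pain with inflammatory signs in more than two joints. Joint tenderness counts as such a sign; arthralgia without one scores zero.
- Myositis needs enzyme, electromyogram or biopsy support. The scheduled chemistry panel in Section 9.2 is ALT, AST and creatinine.
- Fatigue has no item.
- The flare composite is wider. New or worse arthritis without a joint count, an NSAID added for SLE activity, a prednisone increase, or a rise of at least 1.0 in the physician's global score is enough. Each needs a finding or an attribution to SLE that goes beyond the diary entry.
- RAPID3 is a primary safety measure in Section 5.1, but Section 6.3.3 gives it no analysis.

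**4. Scale, for context.** Section 6.1.1.2 uses 3.9% per patient-month and reports 6.1 incidents a year. This can be reproduced: 1 − (1 − 0.039)^12 = 0.3796, and 16 × 0.3796 = 6.07. That is the expected number of participants with at least one flare.
- Post-dose time: 16 participants × 3 doses × 8 days = 384 days, or 384 / 30.44 = 12.6 months.
- Expected chance onsets of any flare: 12.6 × 0.039 = 0.49. P(at least one) = 1 − exp(−0.49) = 0.39.
- With 28-day months and the hazard −ln(0.961) = 0.0398: 13.7 × 0.0398 = 0.55, and the probability is 0.42.
- If the rate of up to 20% in the same section is read as annual (an assumption): 12.6 × [−ln(0.8) / 12] = 0.23, and the probability is 0.21.

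These are flares of every type. The documents give no musculoskeletal share and no share that would present as symptoms alone, so this does not count misfiled events.

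**The case against.** A reader might infer more: that a musculoskeletal lupus flare would be counted as ordinary reactogenicity and escape PSRT review. The documents do not support that.

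- A diagnosed flare, arthritis or myositis is not a listed symptom, so Section 9.8 sends it to the AE log even if its pain is also in the diary. Serious events go there too.
- SLE assessments by a rheumatologist or designee, the flare composite and the separate flare rows of Table 11-8 form an independent route. Footnote b is not attached to those rows.
- Footnote b removes only immediate notification and prompt review, and only at Grade 3. Weekly PSRT review continues through the injection phase (Section 11.4.2), and the Safety Monitoring Board reviews cumulative reactogenicity (Section 11.1.2).
- Clinically, a participant who reports "any postvaccination reaction greater than mild is seen by a clinician within 48 hours after onset, unless the reaction is improving" or it has resolved. Daily maximum severity is collected within the window, and symptoms are followed afterwards.
- Section 11.2.2 says that myositis in SLE usually appears as weakness rather than pain, so the lack of scheduled muscle enzymes is a weak argument.

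Nor do simple counts measure the problem. Three 8-day windows in 364 days, or one participant in 16, are not misclassification rates. The flare counts in Section 4.1.2 (3/28, 7/62, 4/20, 20/72) cover all flare types. The last comes from a study that enrolled moderate to high disease activity, whereas this trial excludes a SELENA-SLEDAI above 4. The same section reports 13 studies with flare rates similar to those of unvaccinated patients.

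All of this stands and narrows the point. It does not close it, because no part of the flare route ensures that a persistent symptom which nobody labels as flare is logged or reported with its duration.

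**Conclusion.** The point holds in a limited form. A non-serious listed systemic symptom with onset on days 0 to 7 is kept on the reactogenicity form whatever its duration, and it is summarised only by maximum grade. At Grade 3 it falls outside immediate notification and prompt PSRT review. Recognised flares should be caught. What can be lost is persistent arthralgia without inflammation, myalgia without myositis findings, or fatigue: absent from the AE tables and, in the reactogenicity table, no different from a one-day reaction.

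A related reporting gap is that recognised flares have no planned table of their own. Table 11-8 also ties its mild and moderate definitions to a rheumatologist's determination about prednisone treatment, and a single mild or moderate flare is reviewed promptly only if judged related.

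The number of participants affected cannot be derived from the documents. The only scale available is about 0.2 to 0.55 chance flare onsets of any type in the post-dose windows, and the cases at issue would be some unknown part of that. The conclusion rests on reading Section 9.8 literally and on reactogenicity records staying out of the AE tables. It is a gap in recording and reporting that is cheap to close, not a failure of safety oversight.

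**What to change.** - **Section 9.8:** also enter on the AE log any listed systemic symptom still present after day 7, or attributed to SLE flare, with onset date, end date, grade and relationship.
- **Section 6.3.3.1:** add, for each symptom, the number of participants in whom it lasted more than 7 days.
- **Section 6.3.3.4:** tabulate all flares by time since last dose, not only discontinuations due to related flares. The table needs one stated flare definition. Section 6.1.1.2 uses a SLEDAI rise of 4 or more and Appendix G a rise of 3 or more, and these must be reconciled.
- **Table 11-8, footnote b:** the sponsor should reconcile it with Section 9.8 and state whether it is meant to cover symptoms that persist beyond the 7-day reactogenicity period. No change to the review or pause rule is proposed.

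The cost is a few more AE-log entries, some symptoms appearing in both the reactogenicity and AE tables (a footnote can say so), and a slightly less favourable AE count. Sample size, visits and blood draws are unchanged.
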